### **8.3.2. Schedule of Visits and Assessments**

Treatment and Follow-up Visits are summarized below; for full details see Section 5.1 for the Schedule of Events.

**During Treatment:** Subjects will have 4 clinic visits during Cycle 1 (Days 1, 5, 12, and 15) and clinic visits every 3 weeks on Day 1 of every cycle thereafter. Subjects who continue past Cycle 13 will have clinic visits every 6 weeks on Day 1 of every other cycle (Cycles 14, 16, 18, etc.).

Safety assessments will be conducted at each clinic visit.

Subjects will have efficacy assessments (CT/MRI) performed at the end of Cycles 2, 4, and 6 (each  $\pm$  3 days). If FDG-PET/CT is acquired at baseline, follow-up FDG-PET/CT imaging at Cycle 4 and at Cycle 10 is required. Scans will be sent for a central radiographic review. Subjects who continue to receive CUDC-907 after Cycle 6 will have a disease assessment (CT/MRI) performed every 12 weeks  $\pm$  1 week (i.e., Cycles 10, 14, 18) until Cycle 18 in the first 12 months with scans collected through the first year, then every 24 weeks  $\pm$  2 weeks (i.e., Cycles 26, 34) until PD or death, or up to 2 years, whichever occurs first. After that, disease assessments may be performed as clinically indicated (i.e., at the discretion of the Investigator or per standard of care).

**During Post-Treatment Follow-Up:** All subjects will have PFS and survival assessments every 12 weeks during the first 6 months, then every 24 weeks until PD or death, or up to 2 years, whichever occurs first. After that, disease assessments may be performed as clinically indicated (i.e., at the discretion of the Investigator or per standard of care). Overall survival may be checked by phone every 3 months and data entered in the electronic case report form (eCRF).

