Definitions: ALT = alanine aminotransferase; AST = aspartate aminotransferase; BUN = blood urea nitrogen; C = cycle; CBC = complete blood count; CT = computed tomography; d = day (s); diff = differential; ECG = electrocardiogram; ECOG = Eastern Cooperative Oncology Group; eCRF = electronic case report form; EOT = End of Therapy; FISH = fluorescence *in-situ* hybridization; FDG-PET = F-fluorodeoxyglucose-positron emission tomography; F/U = follow-up; ICF = informed consent form; IHC = immunohistochemistry; IPI = International Prognostic Index; LDH = lactate dehydrogenase; MRI = magnetic resonance imaging; PD = progressive disease; PET = positron emission tomography; PFS = progression-free survival; PK = pharmacokinetic; q12 = every 12; q24 = every 24; SAEs = serious adverse events

Footnotes:

1. The window for all treatment assessments/procedures is  $\pm 2$  days. If extenuating circumstances prevent a subject from starting or completing treatment, or a scheduled procedure or assessment within the protocol-specified time, the subject may continue to be treated on the study only with permission of the Curis Medical Monitor or designee clinician.
2. Physical exam, performance status, weight, CBC w/differentials and serum chemistry labs may be performed up to 3 days prior to Day 1 of each cycle. Subjects who continue past Cycle 13 will only be required to have a Day 1 visit at the beginning of every other cycle (14, 16, 18, etc.). The Cycle 1, Day 1 physical examination is not required if the screening physical examination was conducted within 3 days prior to administration of the first dose of study drug (Cycle 1, Day 1).
3. Subjects will be required to submit archival tissue samples (most recent available) or fresh tumor samples for central FISH and IHC testing. For subjects with unconfirmed MYC-altered disease, fresh tumor samples (obtained from biopsy-accessible lesions with less than 2% estimated risk for serious complications) are preferred.
4. Performed until time of disease progression, withdrawal of consent, or any other criteria that would make the subject unable to be followed for disease response.
5. Vital signs include blood pressure, heart rate, respiratory rate, temperature, and weight.
6. A serum or urine pregnancy test will be performed for women of childbearing potential at least once per cycle prior to dosing, or more frequently as clinically indicated, as well as during Screening and at the EOT visit.

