This discussion has thus far centered on the implications of *MYC*-altered status for patients with *de novo* DLBCL. In the setting of RR DLBCL in general, there are diminishing prospects for disease control (median OS of 4 to 13 months). The prognosis for patients with RR *MYC*-altered DLBCL is even more discouraging. The outcome of patients with DH disease who don't respond to induction or progress after initial response is very poor, with reported 12-month post-progression survival of 20% (Oki et al, 2014), and median post-progression OS of 17 months following salvage therapy (Petrich et al, 2014). Retrospective analysis of the CORAL trial (Gisselbrecht et al, 2011) was performed to identify the prognostic significance of *MYC* aberrations in patients with RR DLBCL treated with chemotherapy followed by autologous stem cell transplantation (SCT). Four-year OS was 29% in 27 patients who were *MYC*+ versus 62% for those with no *MYC* aberration (21 of these cases were also identified as DH) (Cuccuini et al, 2012).

Analysis of outcomes makes it clear that traditional approaches to relapsed DLBCL are not effective in *MYC*-altered DLBCL. It is recommended that patients with *MYC*-altered B-cell lymphomas in need of further therapy be enrolled into prospective investigational protocols evaluating novel agents with either sound preclinical rationale or demonstrated activity in *MYC*-driven lymphomas (Cheah et al, 2015).

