## 10.6. Concomitant Medications

Information on concomitant medications will be collected from 30 days prior to study drug dosing through the EOT visit. Information on subsequent anticancer treatments will be collected through the Follow-up visits.

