### **11.3.3. Survival Status**

Information on survival status will be collected for all subjects at the Post-Treatment Follow-up Visit time points.

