### **13.3. Post-Treatment Follow-up Visits**

#### **13.3.1. Follow-up Visits $\leq$ 6 Months (Every 12 Weeks)**

- Symptom-directed physical examination (performed until time of disease progression, withdrawal of consent, or any other criteria that would make the subject unable to be followed for disease response)
- IPI score
- Lymphoma assessment (includes physical examination, a review of the subject's current signs and symptoms, B symptoms, and concomitant medications)
- Radiologic assessment (CT/MRI)
- Survival status
- Update concomitant medications (anti-cancer therapies only)
- Collect AEs (only treatment-related SAEs will be captured)

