#### **14.4.3. Efficacy Analyses**

The primary analyses of efficacy will be based on the ITT Population. The interim analyses will be performed on the Evaluable Population.

The primary efficacy endpoint, ORR, will be based on the proportion of subjects with CR or PR using the central determination of disease response in Groups A and B, separately. The estimate will be accompanied by a two-sided exact binomial 95% CB.

Progression-free survival, OS, and DOR will be summarized descriptively for Groups A and B using the Kaplan-Meier method. For such subjects, the progression or censoring date will be determined based on described conventions ([Food and Drug Administration, 2007](#)).

Progression-free survival, median PFS, and the estimated rate at 6 months (PFS6) based on the Kaplan-Meier analyses will be reported separately for Groups A and B. For OS, the estimated rates at 3, 6, 9, and 12 months based on the Kaplan-Meier analyses will be reported for Groups A and B. For DOR, the estimate of the median based on the Kaplan-Meier analyses for Groups A and B will be reported.

Waterfall plots will be used to depict graphically the maximum decrease from baseline in the sum of the product diameters in measurable nodes and nodal masses.

Secondary analyses of efficacy will be conducted based on the ITT and Evaluable Populations using response as determined by both the central determination of disease response and investigator site. In these analyses, the primary efficacy endpoint, ORR, will be estimated using the proportion of subjects with CR or PR. The estimate will be accompanied by a two-sided exact binomial 95% lower CB.

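### The protocol both ends survival follow-up at progression and requires it for all subjects; under the first reading the OS rates are informatively censored

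*Combined protocol and SAP*

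**What the plan says.** Section 8.3.2 says of the period once dosing has stopped: "All subjects will have PFS and survival assessments every 12 weeks during the first 6 months, then every 24 weeks until PD or death". A two-year cap applies if that is sooner. Disease assessments are discretionary after that, and then: "Overall survival may be checked by phone every 3 months", with entry in the eCRF. The synopsis has the same text. So does footnote 11 of the Schedule of Events (5.1), which is attached to the Survival status row.

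Other places set no progression limit on survival status:

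- Section 11.3.3: "Information on survival status will be collected for all subjects at the Post-Treatment Follow-up Visit time points".
- Schedule of Events, footnote 4: "Performed until time of disease progression, withdrawal of consent, or any other criteria that would make the subject unable to be followed". It is attached to the follow-up examination, lymphoma and imaging rows, not to Survival status.
- Sections 13.3.1 and 13.3.2 list survival status without a limit, although the examination in the same lists has one: "Symptom-directed physical examination (performed until time of disease progression, withdrawal of consent".
- Section 10.6: "Information on subsequent anticancer treatments will be collected through the Follow-up visits".

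Progression ends treatment (8.4, 9.3.1). Section 14.4.3 plans this OS output: "For OS, the estimated rates at 3, 6, 9, and 12 months based on the Kaplan-Meier analyses will be reported". It gives no separate OS censoring rule and refers to cited conventions for progression and censoring dates. Section 14.4.8 rules out imputation unless otherwise stated.

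**The concern.** The text does not settle whether vital status must be collected after progression. If sites follow 8.3.2 and footnote 11, a subject who stops treatment for progression has no required survival contact after the End of Therapy visit, and later vital status depends on calls that are optional.

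Such a subject would be censored soon after progression, and in this disease progression usually precedes death. The censoring is then informative. Kaplan-Meier would overstate OS if the death hazard rises after progression, and could understate it if the hazard falls. With up to 65 sites, practice could also differ between sites. A SAP written later can choose a censoring rule but cannot recover vital status that nobody collected.

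**Working it through.** **The texts side by side**

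| Place | Survival follow-up after progression |
|---|---|
| Synopsis; 5.1 footnote 11; 8.3.2 | Ends at progression, death or two years, whichever is first; calls optional |
| 11.3.3 | Required for all subjects at the follow-up time points |
| 5.1 footnote 4 | Progression limit on other rows, not on Survival status |
| 13.3.1, 13.3.2 | Listed, with no statement on progression |

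Section 11.3.3 does not cure the conflict, because it relies on follow-up time points whose duration 8.3.2 and footnote 11 end at progression. The End of Therapy list (13.2.4) has no survival-status item. Section 14.4.4 lists deaths during treatment or within 30 days of stopping, so the model below treats vital status as known for 30 days after progression.

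**Inputs.** The plan gives no OS figure to reproduce, so this is an illustration. All times are exponential. Assumed: median PFS 3 months; share of PFS events that are deaths d = 0.20; median post-progression survival 3 or 5 months; known-status window g = 30 days = 0.986 months. The hazards are h = ln2/3 = 0.2310 for PFS events, and m = 0.2310 or ln2/5 = 0.1386 for death after progression. The resulting median OS is 6.4 or 8.0 months, inside the 4 to 13 months cited in 6.1.1.1.

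**True OS.** S(t) = e^(−ht) + h(1−d)(e^(−mt) − e^(−ht))/(h−m), which becomes e^(−ht)[1 + h(1−d)t] when m = h. At 12 months:

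- post-progression median 3: 0.0625 × (1 + 0.2310 × 0.8 × 12) = 0.0625 × 3.218 = 20.1%
- post-progression median 5: 0.0625 + (0.1848/0.0924) × (0.1895 − 0.0625) = 31.6%

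**What Kaplan-Meier shows with no calls.** Once t exceeds g, the ratio of recently progressed to not-yet-progressed subjects under observation is constant: R = h(1−d)(e^((h−m)g) − 1)/(h−m), or h(1−d)g when m = h. The observed hazard is (dh + mR)/(1 + R). For post-progression median 3:

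- R = 0.1848 × 0.986 = 0.182
- hazard = (0.0462 + 0.2310 × 0.182)/1.182 = 0.0747
- e^(−12 × 0.0747) = 40.8%, which becomes 41.4% once R is allowed to build up over the first 30 days

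If a share q is phoned, replace R by P(t)/e^(−ht). Here P(t) is q times all subjects alive after progression plus (1−q) times those within 30 days of it. The hazard is then integrated numerically.

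Each cell gives the result for post-progression median 3 / 5 months:

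| Month | True OS | No calls | Half phoned | 80% phoned |
|---|---|---|---|---|
| 3 | 77.7 / 82.0% | 81.0 / 83.9% | 79.2 / 82.8% | 78.3 / 82.3% |
| 6 | 52.7 / 62.1% | 64.7 / 69.8% | 57.3 / 64.9% | 54.3 / 63.0% |
| 9 | 33.3 / 44.9% | 51.7 / 58.2% | 39.1 / 48.9% | 35.2 / 46.2% |
| 12 | 20.1 / 31.6% | 41.4 / 48.4% | 25.6 / 35.7% | 21.8 / 32.9% |

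The 12-month error is +21.3 / +16.8 points with no calls, +5.5 / +4.1 with half phoned and +1.7 / +1.3 with 80% phoned. For scale, the standard error at n = 50 with complete follow-up is √(0.201 × 0.799/50) = 5.7 points or √(0.316 × 0.684/50) = 6.6 points.

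**Anchors from the protocol.** Section 6.1.1.2 cites, for double-hit disease, a "reported 12-month post-progression survival of 20" percent. That implies a median of 12 × ln2/ln5 = 5.17 months, and 12-month OS of 48.8% with no calls or 36.4% with half phoned, against 32.5%. The same section also cites a 17-month post-progression median. That gives 58.0% against 59.7%, a slight reversal, but median OS is then 16.3 months, outside 4 to 13.

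**Direction.** The bias is zero when dh = m, that is, when the post-progression median equals the PFS median divided by d. Here that is 3/0.20 = 15 months; with d = 0.30 it is 10 months.

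**Wider ranges.** With PFS median 2–4 months, d 10–50%, post-progression median 3–10 months and median OS kept within 4–13 months, the 12-month error runs from −12.6 to +29.6 points with no calls and from −3.0 to +8.7 with half phoned. A second set used PFS/OS medians of 1/4, 3/7, 5/9 and 10/13 months, d of 10% or 30%, and status known for one month after progression. With no calls the error was upward in 7 of 8 cases, ranging from −4.3 (10.9 − 15.2) to +28.8 (64.3 − 35.5).

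**The case against.** The documents can be read as intending survival follow-up after progression. Section 11.3.3 is the dedicated section and is mandatory. Footnote 4 would be redundant if visits stopped at progression. The sentence that follows the stop in 8.3.2 speaks only of disease assessments, which suggests the stop was meant for those. The telephone sentence has its own interval and no progression limit, so its permissive wording may concern only the mode of contact. On that reading the defect is one loosely worded sentence repeated three times. The no-calls scenario also needs every site to ignore 11.3.3; with half phoned, the base-case error is below one standard error. OS is descriptive, and its censoring rule can still go into the SAP.

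Much of this is fair. Sections 13.3.1 and 13.3.2 are merely silent, since they also omit the limit for lymphoma and imaging assessments, which footnote 4 does limit. Section 10.6 would equally fit subjects who stop without progression. Both are weak evidence that visits continue after progression, but discounting them weakens only the lenient reading. Footnote 11 is still on the Survival status row, its stop covers PFS and survival jointly, and no passage explicitly makes survival contact after progression mandatory. A site that reads literally would stop.

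**Conclusion.** The inconsistency is real and should be fixed while data can still be collected. In the base case the 12-month OS rate is overstated by about 17 to 21 points with no calls, 4 to 6 with half of subjects phoned, and under 2 with 80% phoned. These sizes rest on assumed exponential times, an assumed share of deaths among PFS events and assumed contact rates. The sign is usually upward but not guaranteed. The consequence is confined to a secondary, descriptive endpoint: the primary ORR, its confidence interval and the interim rule do not depend on it.

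**What to change.** In the synopsis, 8.3.2 and footnote 11, apply the progression stop to disease assessments only. Replace the optional telephone sentence with: *Survival status will be collected by visit or telephone every 3 months for all subjects until death, withdrawal of consent or study end, regardless of progression or new anticancer therapy.* Define study end; keeping the present two-year limit would still cover the planned 12-month rates. Align 11.3.3, 13.3.1 and 13.3.2 with that sentence. In 14.4.3, state that OS is censored at the date last known alive, not at progression or at the start of new therapy.

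The cost is wording changes plus one contact every three months per living subject, a modest added site workload after progression. The protocol already foresees the calls and their entry in the eCRF.

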### **8.4. Planned Duration of Treatment**

CUDC-907 will be taken until disease progression, withdrawal from study, unacceptable toxicity, pregnancy, initiation of another anticancer or experimental therapy, noncompliance with study procedures, or study discontinuation.

Dose and/or schedule intensity of CUDC-907 may be reduced due to toxicity.

## 9. SELECTION AND WITHDRAWAL OF SUBJECTS

### 9.1. Patient Inclusion Criteria

1. Age  $\geq$  18 years.
2. At least 2 but no more than 4 prior lines of therapy for the treatment of *de novo* DLBCL and ineligible for (or failed) autologous or allogeneic SCT (salvage therapy, conditioning therapy and maintenance with transplant will be considered one prior treatment).  
**NOTE:** For follicular lymphoma transformed to DLBCL (t-FL/DLBCL), single agent non-cytotoxic therapy will not be considered as a line of therapy.
3. Histopathologically confirmed diagnosis of one of the following:
  - RR DLBCL per the 2008 World Health Organization (WHO) classification of hematopoietic and lymphoid tumors (Swerdlow et al, 2008).
  - HGBL, with MYC and BCL2 and/or BCL6 rearrangements or DLBCL, NOS per the 2016 revision of the WHO classification of lymphoid neoplasms (Swerdlow et al, 2016).
  - Diagnosis of t-FL/DLBCL is allowed. However, other B-cell lymphomas including other transformed indolent lymphomas/DLBCL per the 2008 WHO classification, HGBL, NOS per the 2016 WHO classification, and Burkitt lymphoma are not eligible.
4. Confirmed availability of viable tissue (defined as most recent available archival tumor tissue available, or fresh tumor samples) for central laboratory FISH and IHC testing prior to study dosing. For subjects who enter the study with unconfirmed MYC-altered disease, fresh tumor samples are preferred.  
**NOTE:** To facilitate early testing of MYC status, a separate informed consent form (ICF) specific for MYC testing will be available to be signed prior to sample testing and the signing of the main ICF.
5. CT scan showing at least 1 or more clearly demarcated lymph node(s) with a long axis  $>$  1.5 cm and short axis  $>$  1.0 cm **or** 1 clearly demarcated extranodal lesion(s) with a long axis  $>$  1.0 cm and short axis  $>$  1.0 cm. Baseline FDG-PET scans, if used, must demonstrate positive lesions compatible with CT-defined anatomical tumor sites.
6. Presence of RR disease per Revised Response Criteria for Malignant Lymphoma (Cheson et al, 2007).
  - Relapsed disease is defined by DLBCL confirmed by excisional/incisional biopsy (preferred) or fine needle aspiration (FNA) or core needle biopsy (CNB) after a CR or unconfirmed complete response (CRu).
    - For relapse during prior treatment, biopsy/FNA reconfirmation of the lymphoma is recommended but not mandatory.
  - Refractory disease is defined by (a) PD during prior treatment, (b) stable disease (SD) after  $\geq$  3 cycles of prior treatment, or (c) PR after  $\geq$  6 cycles of prior treatment, or for stage II disease,  $\geq$  3 cycles of treatment and definitive involved field radiotherapy.

- For sustained PR after prior treatment, confirmation biopsy for DLBCL is preferred. An FNA may be acceptable, but if inappropriate (e.g., due to biopsy inaccessibility), the Sponsor may determine eligibility following review of imaging results and disease history.
  - For SD or PD after prior treatment, reconfirmation of DLBCL by biopsy (preferred) or FNA is recommended but not mandatory.
7. Eastern Cooperative Oncology Group (ECOG) performance status of  $\leq 2$ .
  8. Recovery to Grade 1 or baseline of any toxicity due to prior anticancer therapies (excluding alopecia).
  9. Absolute neutrophil count (ANC)  $\geq 1,000/\mu\text{L}$ ; platelets  $\geq 75,000/\mu\text{L}$ ; creatinine  $\leq 1.5 \times$  upper limit of normal (ULN) or calculated creatinine clearance  $\geq 50$  mL/minute as determined by Cockcroft-Gault (using actual body weight) or by 24-hour urine collection measurements of creatinine; aspartate aminotransferase (AST) and/or alanine aminotransferase (ALT)  $\leq 2.5 \times$  ULN; total bilirubin  $\leq 1.5 \times$  ULN or  $\leq 3$  ULN for patients with documented Gilbert's syndrome. Platelet transfusions and administration of granulocyte colony-stimulating factors to help patients meet eligibility criteria are not allowed within 1 week prior to screening complete blood count (CBC) and Cycle 1, Day 1 treatment.
  10. Women of childbearing potential must have a negative serum or urine pregnancy test (not applicable after bilateral oophorectomy)
  11. Men and women of childbearing potential and their partners must agree to use adequate birth control throughout their participation in the study and for 30 days following the last study treatment. Adequate contraception is defined as hormonal birth control, intrauterine device, double barrier method or total abstinence. Acceptable methods of contraception are described in [Table 3](#).
  12. In the Investigator's judgement, able to provide written informed consent and follow protocol requirements.

## 9.2. Patient Exclusion Criteria:

1. Known primary mediastinal, ocular, epidural, testicular or breast DLBCL.
2. Patients must not have active CNS involvement of their malignancy. Patients with prior brain metastases are permitted, but must have completed treatment and have no evidence of active CNS disease (clear cerebrospinal fluid [CSF]) for at least 4 weeks prior to the first dose of CUDC-907. Intrathecal chemoprophylaxis to prevent the emergence or recurrence of lymphoma in the CNS is permitted on study and may be administered per institutional guidelines.
3. Known allergy or hypersensitivity to PI3K inhibitors or any component of the formulations used in this study.
4. Cytotoxic anticancer therapy (e.g., alkylating agents, anti-metabolites, purine analogues) within 2 weeks of study entry.
5. Radiotherapy delivered to non-target lesions within one week prior to starting study treatment or delivered to target lesions that will be followed on the study (note: prior sites of radiation will be recorded).

6. Treatment with experimental therapy within 5 terminal half-lives ( $t_{1/2}$ ) or 4 weeks prior to enrollment, whichever is longer.
7. Current or planned glucocorticoid therapy, with the following exceptions:
  - Doses  $\leq 1$  mg/kg/day prednisolone or equivalent glucocorticoid and inhalational therapies for mild chronic obstructive pulmonary disease (COPD) or asthma are allowed.
  - Replacement dosing of steroids (defined as  $< 30$  mg/day hydrocortisone or the equivalent) is allowed, provided that the steroid dose has been stable or tapering for at least 14 days prior to the first dose of CUDC-907.
8. Graft versus host disease following transplant within 100 days prior to study treatment.
9. Major surgery, other than diagnostic surgery, occurring 4 weeks prior to study treatment.
10. Diabetes mellitus that is not controlled with medication.
11. Serious infection requiring intravenous antibiotic therapy within 14 days prior to study treatment.
12. Uncontrolled or severe cardiovascular disease, including myocardial infarction, unstable angina, or atrial fibrillation (AFib) within 6 months prior to study treatment, New York Heart Association (NYHA) Class II or greater congestive heart failure, serious arrhythmias requiring medication for treatment, clinically significant pericardial disease, cardiac amyloidosis, or QTc with Fridericia's (QTcF) correction that is unmeasurable or  $\geq 480$  msec on screening electrocardiogram (ECG). (Note: for QTcF  $\geq 480$  sec on the screening ECG, the ECG may be repeated twice at least 24 hours apart; the mean QTcF from the three screening ECGs must be  $< 480$  msec in order to meet eligibility for trial participation).
13. Gastrointestinal disease or disorder that could interfere with the swallowing, oral absorption, or tolerance of CUDC-907. This includes uncontrolled diarrhea ( $> 1$  watery stool/day), major abdominal surgery, significant bowel obstruction and/or gastrointestinal diseases that could alter the assessment of PK or safety, including but not limited to: irritable bowel syndrome, ulcerative colitis, Crohn's disease and hemorrhagic coloproctitis.
14. History of other invasive malignancy, unless adequately treated with curative intent and with no known active disease present within 1 year prior to the first dose of study drug, provided it is deemed to be at low risk for recurrence by the treating physician.
  - These conditions include but are not limited to non-melanoma skin cancer, carcinoma *in situ*, (including superficial bladder cancer), cervical intraepithelial neoplasia and organ-confined prostate cancer.
15. Known infection with human immunodeficiency virus (HIV).

16. Known active or chronic hepatitis B virus (HBV) or hepatitis C virus (HCV) infection.
  - Regardless of hepatitis B surface antigen (HBsAg) status, if hepatitis B core antibody (HBcAb) is positive, then HB DNA testing will be performed and if positive the patient will be excluded.
  - Regardless of hepatitis RNA level, patients who are positive for hepatitis C antibody (anti-HCV) will be permitted to enroll provided that they meet all eligibility criteria and are without evidence of cirrhosis. Patients diagnosed with HCV < 6 months prior to enrollment will be considered to have acute HCV and excluded unless viral load is undetectable.
17. Pregnant or breast-feeding women.
18. Unstable or clinically significant concurrent medical condition that would, in the opinion of the Investigator, jeopardize patient safety and/or compliance with the protocol.

